CXC	chemokine of cysteine -X- cysteine type
C3M	collagen degradation markers
CRPM	c-reactive protein degraded by MMP
DLco	diffusion factor for carbon monoxide
EL-M7	MMP-7 generated elastin fragments
FEV1/FVC	forced expiratory volume/forced vital capacity
GDPR	General Data Protection Regulation
KL-6	Krebs von den Lungen 6
IgE	immunoglobulin E
IL	interleukin
IPF	interstitial pulmonary fibrosis
MDT	multi-disciplinary team
MLF	mucosal lining fluid
MMP	matrix metalloprotease
MSD	Meso Scale Discovery
NAC	nasal allergen challenge
NS	nasosorption
SAE	serious adverse event
SAM	synthetic absorptive matrix
SP	surfactant protein
sRAGE	soluble receptor for advanced glycation end products

KEYWORDS

Idiopathic pulmonary fibrosis, biomarkers, mucosal lining fluid, nasosorption, bronchosorption, cytokines, chemokines,

STUDY SUMMARY

TITLE	FIBRO-SAM: Development of Airway Absorption Sampling Methods for Biomarker Assessment in Probable Idiopathic Pulmonary Fibrosis (IPF) Patients
DESIGN	Observational study with opportunistic airway sampling in patients with probable Idiopathic Pulmonary Fibrosis and Sarcoidosis, who are undergoing bronchoscopy as part of their diagnosis and/or monitoring
AIMS	To assess molecules reflecting pulmonary fibrosis using novel upper and lower airway sampling methods of absorption; nasosorption, (upper airway) and bronchosorption (lower airway).
OUTCOME MEASURES	Comparing levels of mediators including periostin, surfactant protein D (SPD), CCL18, CXCL13 in blood, nasal and bronchial airway mucosal lining fluid.
POPULATION	Probable Idiopathic Pulmonary Fibrosis patients (IPF) undergoing bronchoscopy, n = 30 Sarcoidosis patients, n = 15 Healthy volunteers, n = 15
ELIGIBILITY	Adults (aged 40 to 85 years) will need to meet inclusion and exclusion criteria. Patients in this study will be selected at the time of their scheduled clinical bronchoscopy at St Mary's Hospital at Imperial College Healthcare Trust and all Healthy controls will be recruited by approaching carers and partners of recruited patients as well as advertising in hospital OPA, public places and local media
DURATION	Clinical Phase: March 2020 to March 2021 (estimated)

Contents

1	INTRODUCTION	8
	Synthetic absorptive matrix (SAM):	9
	Nasosorption after nasal allergen challenge.....	9
	Bronchosorption:	9
2	STUDY SUMMARY	10
3	STUDY OBJECTIVE.....	12
3.1	Research Question and Hypotheses.....	12
3.2	Primary Outcome.....	12
3.3	Secondary Outcomes	12
4	STUDY DESIGN AND SAMPLE COLLECTION	13

12 PUBLICATION POLICY27

1 INTRODUCTION

Idiopathic Pulmonary Fibrosis (IPF) is a progressive and incapacitating lung disorder that has a variable clinical course, but is generally fatal within a few years (1, 2). The diagnosis of IPF is based on clinical features, lung function tests showing interstitial disease (decreased transfer of carbon monoxide) and usual interstitial pneumonia (UIP) on high resolution computerised tomography (HRCT) scan of the lung fields (3, 4). As part of their diagnostic work up, most patients with probable IPF require bronchoscopy for taking broncho-alveolar lavage (BAL) samples.

Therapy for IPF is gradually being developed with drugs such as pirfenidone (5) and nintedanib (6) showing modest effects. However, the variable and pleiotropic nature of IPF suggests that combination and personalised therapy will be required (7). In recent years, there have been extensive efforts to measure blood biomarkers in this disease, and a number of blood biomarkers have been described in IPF:

- MMP-7, ICAM-1, VCAM-1, CXCL8/IL-8, S100A12 (8)
- surfactant proteins (SP)-A & D (9, 10)
- periostins (11)
- KL6 (12)
- antibodies to heat shock protein (HSP) 70 (13)
- soluble receptor for advanced glycation end products (sRAGE) (14)
- CCL18 (15), CXCL13 (16)
- collagen biomarkers and protease degradation products (collagen neo-epitopes) (17)
- CA19-9 and CA125

Very recently a 52 gene expression profile in blood has been found to be predictive of outcome in IPF (18).

In IPF there is an urgent need to develop new methods for taking lung samples from a bronchoscope to measure mucosal inflammation. Inflammatory mediators in the mucosal lining fluid (MLF) reflect underlying inflammation, but existing bronchoscopic methods (BAL and biopsy) have significant drawbacks.

Bronchosorption involves passing a special medical sampling device down the operating portal of the bronchoscope. Using bronchosorption to obtain samples and identify molecular signatures of respiratory disease, we hope to achieve new fundamental insights and refine the investigation, diagnosis, stratification and monitoring of IPF. We can discover biomarkers to help assess the effects of existing therapies and identify potential targets for novel treatments.

In addition to BAL samples being taken from the bronchoscope for clinical diagnostic purposes, in this study we shall perform upper airway sampling (nasosorption) and this will be compared with the lower airway sampling of bronchosorption.

This study is being carried out for clinical research purposes, is optional for patients, and is unlikely to benefit the patient personally. This study is unlikely to change the clinical diagnosis of a patient and will not change their drug treatment.

Absorption of Airway Mucosal Lining Fluid with Synthetic Absorptive Matrix (SAM)

Synthetic absorptive matrix (SAM)

SAM strips are like blotting paper and are now widely used to obtain nasal MLF by nasosorption having first been used in 2003 (19, 20). These absorbent materials are comfortable to use and can obtain MLF even from inflamed noses at frequent intervals over extended periods of time. There is minimal protein binding to the SAM strip, and proteins in the fluid can be efficiently eluted.

Nasosorption

After a nasal allergen challenge, we have used the technique of nasosorption to absorb mucosal lining fluid from the nose at frequent intervals. Nasosorption uses a small strip of absorbent material on a handle to soak up fluid from the inside surface of the nostril. Nasosorption is a CE marked device that uses medical grade materials and is produced in a specialised medical device manufacturing company. This is placed inside the nostril and left for 60 seconds, keeping light pressure with a finger to absorb fluid before being removed. This technique is very gentle and minimises rubbing and brushing inside the nostril. The material absorbs the fluid and chemicals produced by the nasal cells that can then be extracted and measured. After nasal allergen challenge (NAC) the eluate from nasosorption contains inflammatory mediators, cytokines and chemokines at high detectable levels, and this has been shown after NAC with grass pollen (21, 22), cat allergen (23) and lipopolysaccharide (24). A recent manuscript has described full gene expression changes after NAC with grass pollen (25) In addition, following experimental human rhinovirus (HRV) challenge in asthma patients, nasosorption and bronchosorption were performed to measure IL-15 (26), IL-25 (27), IL-33 (28) and IL-18 (29). A very complete profile of cytokines and chemokines following HRV challenge in asthma has recently been reported (30) (31), and viral load and cytokines have been measured after RSV bronchiolitis of infancy (32). An extensive validation study has been carried out comparing performance of nasosorption with nasal lavage (33).

Bronchosorption:

The Respiratory Medicine group in Imperial College have developed a bronchosorption device that employs a different proprietary medical grade soft fibrous SAM at the tip. The bronchosorption device is now CE-marked and has been used in over 1500 patients and healthy volunteers. Bronchosorption has the advantage of being less invasive and causing less dilution than a bronchoalveolar lavage (BAL). A straw of SAM or synthetic sponge is attached to a leading plastic wire, and placed down a sheath within the operating portal of a bronchoscope. Under direct bronchoscopic vision the SAM is advanced against the mucosa of a main bronchus or segmental bronchus for up to 30 secs, under direct vision the SAM is then withdrawn up the sheath, and MLF eluted from the detached SAM. The eluted MLF may then be analysed for

levels of inflammatory mediators: such as a panel of chemokines and cytokines using the MSD analyser. High detectable levels of mediators of inflammation can then be measured in the bronchial MLF. [name] [name] of the Department of Respiratory Medicine at Saint Mary's Hospital has an extensive experience of successfully sampling over 1000 patients to collect over 1000 bronchosorption samples. The procedure is well tolerated and up to 40µl of fluid is absorbed on a single occasion. The bronchosorption kit is supplied in sterile packs, and has undergone durability and functional testing, and is supplied sterilised by gamma irradiation. In the HRV infection model in patients with allergic asthma and healthy controls, both nasosorption and bronchosorption have been carried out to measure IL-15 (26), IL-25 (27), IL-33 (28) and IL-18 (29). Bronchosorption has been shown to have considerable promise for measuring biomarkers in asthma, and has potential to be used for personalised medicine and selection of specific biologics (30) (31).

[figure not shown]

Figure 1: Bronchosorption device

Bronchoalveolar Lavage (BAL):

As part of the bronchoscopy procedure, the doctor intends to collect a BAL sample. This is done by instilling some sterile fluid into the lung and then drawing this fluid back out again with the bronchoscope. The BAL fluid is then studied to help in the diagnosis of lung diseases. For our study, we will collect this fluid for research purposes.

2 STUDY SUMMARY

In patients are having bronchoscopy with BAL sampling done for their diagnostic work up, we propose bronchosorption samples be also taken during bronchoscopy for patients with probable IPF (n=30) and sarcoidosis (n=15) who agree to take part in this study.. For our clinical research we shall collect BAL and the following additional samples at the bronchoscopy baseline visit: serum, whole blood, and mucosal lining fluid by absorption: nasosorption, bronchosorption and

urine. We will also be collecting serum, whole blood, and nasosorption samples at 3 and 6 month follow-up visits.

In addition we shall study age matched healthy volunteers (n=15) who will not undergo bronchoscopy. From these participants we will collect serum, whole blood, and nasosorption only. Healthy volunteers are included in this study since we need to compare the levels of biomarkers in blood and nasal mucosal lining fluids in patients with probable idiopathic pulmonary fibrosis (IPF) and sarcoidosis with healthy volunteers

We will measure a range of molecules and mediators in the samples collected. We can assess molecules reflecting pulmonary fibrosis in the lungs (BAL), and using novel sampling methods of bronchial mucosal lining fluid (bronchosorption), and also from the upper airway (nasosorption). A critical issue is whether disease in the alveoli and the very small bronchioles will permit molecules to be transmitted by the mucociliary escalator (MCE) up to the larger airways.

Biomarkers in the airways will reflect distal pulmonary fibrosis immunopathology. IPF and sarcoidosis are diseases of fibrosis and granuloma formation and will have different associated biomarkers.

Airway absorption sampling methods and biomarkers can be used to understand molecular mechanisms, diagnose and monitor pulmonary fibrosis. The biomarkers can contribute to personalised medicine through the selection and stratification of patients for specific therapy, to monitor that therapy, and to provide targets for new therapy.

The total study involves a total of 30 subjects with probable IPF, 15 patients with sarcoidosis and 15 healthy volunteers. Recruitment for this study is likely to take between 12 and 24 months. An interim analysis at 12 months will be able to identify any emerging differences in biomarkers between the groups, and allow the nature of biomarkers of inflammation to be adjusted prior to the final analyses. In an exploratory study of novel methods of mucosal sampling in probable IPF and sarcoidosis, we do not know the rate of recruitment, and would prefer not to specify an exact number of patients for when interim analysis is performed.

Biomarkers to be measured:

1. Blood (serum) and MLF

There will be a particular focus on 4 biomarkers:
Periostin, surfactant protein D (SPD), CCL18 and CXCL13

A range of other biomarkers will be measured including the following:

- IL-1 β , IL-2, IL-8 (CXCL8), IL-12, IL-13, IL-17, IL-23, IL-33
- TGF- β , FGF basic, TNF- β , CTGF
- sICAM-1, sVCAM-1, CRP, SAA
- D-dimer and C3a, C5

Other biomarkers of inflammation may also be measured.

2. Whole blood for gene expression (mRNA) and DNA sequencing:

- To examine in peripheral blood expression of genes and or gene signatures related to IPF and disease progression
- To examine genetic loci that contribute to IPF risk and disease progression such as muc5b and TERT

3. Urine

- Collagen fragments and bioactive lipids involved in inflammation, which may include, but are not limited to C3M, pro-C3, CRPM, and EL-M7, may be measured.

3 STUDY OBJECTIVE

3.1 Research Question and Hypotheses

1. Are levels of periostin, surfactant protein D (SPD), CCL18, CXCL13 and other biomarkers in bronchial mucosal lining fluid (MLF) useful as a biomarker for IPF patients?
2. Do levels of mediators in less invasive upper airway samples (nasosorption) correlate with levels in lower airway samples (bronchosorption)?
3. Do airway levels of these mediators add value when used in conjunction with blood biomarkers of IPF?

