3.3 Secondary Outcomes

1. Comparing mediator levels between airway samples (nasosorption and, bronchosorption) within and across the 3 groups (probable IPF, sarcoidosis and healthy controls). Establish significance between groups and correlations across patient groups for sampling types.
2. Comparing mediator levels and mRNA (gene expression) in blood with airway mediator levels across the 3 patient groups, and assessing the degree of correlation.

3. Comparing mediator levels in airway samples and blood with clinical parameters
4. Comparing urine metabolites across the 3 patient groups.

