8.3 Statistical Analysis

Data and all appropriate documentation will be stored for up to 10 years after the completion of the study, including the follow-up period.

The major data will be levels of mediators: periostin, surfactant protein (SPD), CCL18 and CXCL13 in blood and bronchial lining fluid.

We shall perform a test of distribution of data (Shapiro-Wilks test) to check normality of data to ensure appropriate statistical tests are applied to the data.

We shall make individual x-y plots for mediators displaying levels for each individual subject within the patient groups (Probable IPF and sarcoidosis) and healthy controls

Summary Statistics

- Normal data with graphs with means and standard error of means (SEM)
- Non-normal data with graphs with medians, quartiles and ranges (box-whisker)

Paired or unpaired t-tests/ANOVA (or equivalent non-parametric tests) will be used to compare mediator levels in blood and airway mucosal lining fluid within groups over time or between different groups at a single time point.

Correlations will be performed to compare mediator levels in blood, and upper and lower airway mucosal lining fluid samples and clinical parameters in patient groups and healthy controls.

Other graphical and analyses methods like heat maps, violin plots, clustering, multivariate analyses and ROC curves will be used as appropriate.

A *P* value of <0.05 is considered significant.

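### Research question 3 asks whether airway levels add to blood biomarkers, but no outcome or analysis in the plan measures that increment

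*Combined protocol and SAP*

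**What the plan says.** Section 3.1 lists three research questions. The third is: "Do airway levels of these mediators add value when used in conjunction with blood biomarkers of IPF". It is incremental: blood alone against blood plus airway.

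Section 3.3 lists four secondary outcomes, none tied to a numbered question. Item 2 is closest: "Comparing mediator levels and mRNA (gene expression) in blood with airway mediator levels across the 3 patient groups, and assessing the degree of correlation". Item 3 sets airway and blood levels against clinical parameters.

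Section 8.3 plans three kinds of analysis that could bear on the question:
- group tests: "Paired or unpaired t-tests/ANOVA (or equivalent non-parametric tests) will be used to compare mediator levels in blood and airway mucosal lining fluid";
- correlations: "Correlations will be performed to compare mediator levels in blood, and upper and lower airway mucosal lining fluid samples", and with clinical parameters;
- a closing list: "Other graphical and analyses methods like heat maps, violin plots, clustering, multivariate analyses and ROC curves will be used as appropriate".

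The plan gives no blood-only reference model, combined model, classification target for question 3, measure of increment or internal validation. Section 8.1 calls the study exploratory and gives no sample size calculation.

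**The concern.** Question 3 needs a quantity that says how much better a decision becomes once the airway level is known on top of the blood level. Group tests look at one compartment at a time. Correlation says how closely two compartments move together. Neither is an increment. The methods that could yield one, multivariate models and ROC curves, are named without any definition.

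So the question may go unanswered, or be answered by whichever model and AUC look best after the data are seen. Airway sampling could be credited with value that it lacks, or dismissed because it tracks blood. Section 8.1 hopes that the results will support sample size calculations for later studies, so an optimistic increment could carry forward.

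**Working it through.** The documents state no AUC, effect size or power, so there is no figure to reproduce. Effect sizes below are assumptions, shown as ranges.

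**Inputs from the documents.** Probable IPF n = 30, sarcoidosis n = 15, healthy volunteers n = 15 (section 4.2). Healthy volunteers have no bronchoscopy (7.2), so any model with a bronchial level rests on 30 v 15. There are four focus mediators: periostin, SPD, CCL18 and CXCL13 (section 2). The significance threshold is 0.05 (8.3).

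**Step 1: correlation does not fix added value.** For two normal markers with standardised group differences d_b (blood) and d_a (airway) and within-group correlation r, the best linear combination has

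D² = (d_b² − 2·r·d_b·d_a + d_a²) / (1 − r²), AUC = Φ(D/√2).

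Take r = 0.7 and d_b = 0.5. Blood alone: AUC = Φ(0.5/√2) = 0.64.
- d_a = 0.5: D² = (0.25 − 0.35 + 0.25)/0.51 = 0.294; AUC = 0.65; gain about 0.01.
- d_a = 1.0: D² = (0.25 − 0.70 + 1.00)/0.51 = 1.078; AUC = 0.77; gain about 0.13.

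Again with r = 0.9 and blood AUC 0.75: the true gain is +0.006 if the airway marker's own AUC is 0.75, and +0.189 if it is 0.50. One correlation thus goes with negligible or large added value.

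**Step 2: apparent AUC gain from noise at 30 v 15.** Simulation (2,000 data sets per scenario): independent normal markers, one blood marker shifted by d_b SD in IPF, airway markers with no group difference. Logistic models are fitted with and without the airway markers, and both AUCs are taken on the fitting data.

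| Blood effect (SD) | True blood AUC | One noise airway marker: mean gain (share above 0) | Four: mean gain (share above 0) |
|---|---|---|---|
| 0 | 0.50 | +0.04 (80%) | +0.12 (98%) |
| 0.7 | 0.69 | +0.02 (72%) | +0.07 (96%) |
| 1.0 | 0.76 | +0.01 (69%) | +0.05 (96%) |
| 1.4 | 0.84 | +0.01 (66%) | +0.04 (93%) |

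The true gain is nil in every row. With four noise airway markers added to four blood markers, the mean apparent gain is +0.082, +0.057, +0.042 and +0.026 at true blood AUC 0.5, 0.7, 0.8 and 0.9. In new subjects the same models change the AUC by 0.000, −0.029, −0.036 and −0.034.

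**Step 3: does a correction work at this size?** With four blood and four noise airway markers and blood AUC 0.75 (120 data sets, 60 resamples each), bootstrap optimism correction moves the mean gain from +0.046 to −0.011 (5th to 95th percentile −0.081 to +0.086). Most of the bias goes, but the estimate stays imprecise.

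The nested likelihood-ratio test at 0.05 has about 6% false positives for one airway term added to one blood term, and about 12% for four added to four (8 predictors on 15 sarcoidosis patients, 15/8 = 1.9 per predictor). These are ordinary logistic fits; penalised fits were not simulated.

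**The case against.** **No method is assigned to question 3.** A reader might infer that the plan prescribes correlation for added value, and so states the wrong quantity. The documents do not support that. Section 3.3 item 2 stands on its own, does not mention added value, and correlation is a fair way to compare blood with airway levels. Item 3 is about as close to the question, and the multivariate analyses in 8.3 could include a combined model. This stands: the fault is a missing analysis, not a wrong one.

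**Same-sample AUCs are not stated.** A reader might also infer that the study will report unvalidated AUCs fitted and judged on the same 45 patients. Section 8.3 neither says this nor rules out cross-validation. The bias in step 2 is therefore conditional on an analysis that the plan leaves open.

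**The size depends on the model.** Four noise markers on a weak blood marker is an unfavourable case. One airway marker on one blood marker gives about 0.01 to 0.04, and in roughly a fifth to a third of data sets the apparent gain is not above zero. The bias holds on average, not every time. On the other hand, choosing the best of four such pairs of noise markers brings the mean gain back to 0.056 (blood 0.7 SD) or 0.097 (blood zero).

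**The study is exploratory**, and question 3 is neither the primary outcome nor a listed secondary one. This lowers the stakes and leaves the primary IPF v sarcoidosis comparison untouched. It does not supply an analysis for a stated research question.

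**Conclusion.** The point holds as a gap: the plan poses an incremental question and defines nothing that measures an increment. Its firm analyses, group tests and correlations, cannot do so. Its open-ended ones could, but would be biased upward on average if AUC gains were taken from the fitting data: about +0.01 to +0.04 for one noise airway marker added to one blood marker, and +0.05 to +0.12 for four, at blood effects of 0 to 1.0 SD.

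The sizes rest on independent normal markers and assumed blood effects, and they shrink as the blood marker gets stronger. That correlation does not determine added value follows from the formula in step 1. The change is worth making, but the primary outcome does not depend on it.

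**What to change.** Add to section 8.3, under a line naming research question 3, and settle it before the 12-month interim analysis, which section 8.2 allows to alter the biomarker panel:

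1. Target: IPF v sarcoidosis, the contrast of the primary outcome.
2. For each of the four focus mediators, compare two nested penalised (Firth) logistic models: log blood level; log blood plus log bronchial level. Fit the nasal level in a parallel secondary model.
3. Report the (penalised) likelihood-ratio test with a multiplicity adjustment across the four mediators.
4. Report the change in AUC with bootstrap optimism correction and a 95% CI, labelled exploratory. Apply the same correction to any multi-marker AUC.
5. State that each model tests added value over the same mediator in blood, not over the full blood panel, and that it does not address monitoring or selection for therapy.

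**Cost.** Four small models, their nasal counterparts and a bootstrap, with no extra patients or samples: serum, nasosorption and bronchosorption are all scheduled at visit 1 (7.1.1). The reported AUCs will be less favourable and the intervals wide.

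Power is modest. In the step 2 setting with a blood effect of 0.7 SD and an uncorrelated airway marker, the unadjusted test has about 35%, 68% and 84% power at airway effects of 0.5, 0.8 and 1.0 SD (1,500 data sets each). At a Bonferroni level of 0.05/4 = 0.0125 these fall to about 18%, 46% and 67%. A non-significant result should therefore not be read as no added value.
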